Statistical processing	Statistical analyses and graphic visualization were performed using SPSS 26.0 (IBM Corp.) and GraphPad Prism 9.0. Data for normally distributed, skewed distributed, and categorical variables were expressed as mean $\pm$ standard deviation, median (interquartile range), and frequency (%), respectively. Intergroup comparisons of categorical variables were conducted using the Chi-square ( $\chi^2$ ) test or Fisher's exact test, while continuous variables were analyzed using the Student's t-test or Mann-Whitney U test. Variables with $p < 0.05$ in univariate analysis were subsequently included in multivariate logistic regression analysis.  Mediation analysis was performed using the PROCESS macro 4.1, with 1000 bootstrap iterations to decompose the total effect into direct and indirect paths. Receiver operating characteristic (ROC) curve analysis was conducted using SPSS 26.0 to evaluate the predictive performance of individual and combined biomarkers. All analyses adopted two-tailed tests, and $p < 0.05$ was considered statistically significant.
Abbreviation	NEC, necrotizing enterocolitis; PNEC, perforated necrotizing

enterocolitis; VLBW, very low birth weight; SGA, small for gestational age; NICUs, neonatal intensive care units; PDA, patent ductus arteriosus; RDS, Respiratory distress syndrome; CRP, C-reactive protein; WBC, white blood cell; CBC, complete blood count; NEU, absolute neutrophil count; LYM, absolute lymphocyte count; MON, absolute monocyte count; EOS, eosinophilic granulocyte; RBC: red blood cell; PLT, platelet count; MPV, mean platelet volume; PDW, platelet distribution width; NLR, neutrophil-to-lymphocyte ratio; NMR, neutrophil-to-monocyte ratio; MLR, monocyte-to-lymphocyte ratio; SII, systemic inflammatory index =  $(NEU*PLT)/LYM$ ; SIRI, systemic inflammatory response index =  $(NEU*MON)/LYM$ ; AISI, aggregate inflammatory systemic index =  $(NEU*MON*PLT)/LYM$ ; nSOFA, neonatal sequential organ failure assessment; ROC, receiver operating characteristic; AUC, the area under the ROC curve; OR, odds ratio; CIs, confidence intervals.

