## 1. project basis

### 1.1 Research background

Necrotizing enterocolitis (NEC), a life-threatening gastrointestinal disorder predominantly, affects 5–12% of very low birth weight (VLBW) neonates, with 20–40% of cases progressing to severe disease requiring surgical intervention, while survivors often endure lifelong consequences, including short-bowel syndrome and neurodevelopmental impairments [1-4]. Despite advances in neonatal care, early identification of high-risk patients remains challenging due to the nonspecificity of clinical signs (e.g., abdominal distension, feeding intolerance) and radiographic findings (e.g., pneumatosis intestinalis), which frequently manifest only after irreversible bowel damage has occurred [5]. Furthermore, current diagnostic tools or conventional biomarkers lack both sensitivity and specificity for early risk stratification of NEC, underscoring an urgent need for biomarkers that integrate pathophysiological mechanisms to guide preemptive therapeutic strategies.

Emerging evidence underscores the multifactorial pathophysiology of NEC, where intestinal ischemia-reperfusion injury, exaggerated immune activation, and microbial dysbiosis converge to drive disease progression [6]. Hypoxic-ischemic injury constitutes a key pathological mechanism underlying intestinal mucosal damage in NEC, driving dysregulation of cellular processes including apoptosis, autophagy, proliferation, and migration within intestinal tissues [7]. In infants with NEC, persistent hypoxemia and compromised tissue perfusion induce metabolic reprogramming, marked by a shift toward glycolytic dominance—a compensatory adaptation to oxygen deprivation. Within this framework, serum lactate, as a well-established marker of tissue hypoperfusion and anaerobic metabolism, has garnered attention for its prognostic relevance. Elevated lactate levels correlate with transmural intestinal necrosis and predict fatal outcomes in NEC, reflecting the severity of ischemic insult [8,9]. However, lactate alone lacks specificity, as hyperlactatemia may arise from concurrent sepsis or perinatal asphyxia, limiting its standalone utility [10,11]. Recent studies propose combining lactate with

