immune-inflammatory biomarkers (such as intestinal fatty acid binding protein or albumin) to address this limitation [12,13]. Peripheral blood cell analysis serves as a widely accessible and rapid auxiliary diagnostic tool in neonatal intensive care units (NICUs). Dynamic changes in peripheral white blood cell (WBC) counts and subset distribution have been validated as biomarkers closely associated with NEC [14]. Accumulating evidence underscores the involvement of lactate metabolism in immunomodulation and its influence on disease pathogenesis [15]. However, the combined utility of lactate levels and peripheral WBC profiles for NEC diagnosis and prognostic stratification remains unexplored.

As NEC progresses, particularly in cases of perforated NEC, it can evolve from a localized intestinal disease into a systemic illness characterized by a sepsis-like state and multi-organ dysfunction. The Neonatal Sequential Organ Failure Assessment (nSOFA) score is a validated tool designed to objectively quantify the degree of organ dysfunction in critically ill neonates by evaluating the respiratory, cardiovascular, and hematologic systems [16]. Studies have demonstrated that higher nSOFA scores are strongly and independently associated with mortality risk in neonates with respiratory distress syndrome, late-onset sepsis, and NEC [16-18]. However, single nSOFA lacks sufficient sensitivity for severe NEC subtypes like PNEC-specific risk stratification: while it predicts overall NEC mortality and the need for surgical intervention [16], existing studies have not specifically evaluated its performance in distinguishing NEC from non-perforated NEC or predicting PNEC-related mortality. The Lewis et al. [16] study included surgical NEC (e.g., laparotomy or peritoneal drain placement) but did not isolate PNEC as a distinct endpoint, leaving a critical gap in understanding how nSOFA performs in this highest-risk subgroup.

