## 3. Research scheme and technical route

### 3.1 Research Design

The principal investigator (PI) and project leader of this study are [name], chief physician of pediatrics of the Guangzhou Women and Children's Medical Center. In this study, a retrospective analysis was conducted on 220 enrolled neonates with necrotizing enterocolitis (NEC), with data collected from July 1, 2017 to December 31, 2022. Statistical methods including correlation analysis, multivariate logistic regression, mediation analysis, and receiver operating characteristic (ROC) curve analysis were employed to perform mutual analysis of the collected clinical data, laboratory parameters, and prognostic/mortality outcomes. This analysis aimed to identify meaningful biomarkers and establish a predictive model, thereby providing evidence for the pathophysiological mechanisms underlying NEC progression. It is anticipated that this will optimize clinical decision-making for NEC patients and improve the survival rate and quality of life of these neonates.

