### 3.3 data collection

Data collection was performed via structured extraction from electronic medical

records. The following variables were systematically retrieved: (1) Neonatal medical history, including sex, gestational age, birth weight, and history of birth asphyxia (e.g., Apgar scores); (2) Maternal medical history, particularly mode of delivery, chorioamnionitis, and premature rupture of membranes; (3) NEC-related clinical parameters: Bell's staging, clinical manifestations (abdominal distension, bloody stools, pneumoperitoneum), complications (patent ductus arteriosus [PDA], sepsis, shock), therapeutic interventions (mechanical ventilation, surgical treatment), and mortality; (4) CBC parameters, lactate levels, and parameters required for calculating the nSOFA score at the onset of NEC.

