### 3.4 Inclusion criteria

- (1) Diagnosis of NEC and having undergone surgical treatment, confirmed by clinical manifestations (e.g., abdominal distension, bloody stools), radiological evidence (pneumatosis intestinalis, portal venous gas, or pneumoperitoneum), and pathological examination in accordance with established guidelines;
- (2) Availability of complete medical records for data extraction.

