### 3.7 Statistical processing

Statistical analyses and graphic visualization were performed using SPSS 26.0 (IBM Corp.) and GraphPad Prism 9.0. Data for normally distributed, skewed distributed, and categorical variables were expressed as mean  $\pm$  standard deviation, median (interquartile range), and frequency (%), respectively. Intergroup comparisons of categorical variables were conducted using the Chi-square ( $\chi^2$ ) test or Fisher's exact test, while continuous variables were analyzed using the Student's t-test or Mann-Whitney U test. Variables with  $p < 0.05$  in univariate analysis were subsequently included in multivariate logistic regression analysis.

Mediation analysis was performed using the PROCESS macro 4.1, with 1000 bootstrap iterations to decompose the total effect into direct and indirect paths. Receiver operating characteristic (ROC) curve analysis was conducted using SPSS 26.0 to evaluate the predictive performance of individual and combined biomarkers. All analyses adopted two-tailed tests, and  $p < 0.05$  was considered statistically

significant.

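### The mediation analysis names no variables or adjustment; with markers all taken at NEC onset, shared severity alone can produce an indirect effect, so it cannot carry the mechanism wording in 3.1

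*Combined protocol and SAP*

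**What the plan says.** The method gets one sentence in 3.7, repeated in the Abstract: "Mediation analysis was performed using the PROCESS macro 4.1", "with 1000 bootstrap iterations to decompose the total effect into direct and indirect paths". Neither place names an exposure, a mediator, an outcome, a model or a covariate. The only covariate rule in 3.7, a univariate screen at 0.05, is stated for the logistic regression and not for mediation.

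Section 3.1 lists "Statistical methods including correlation analysis, multivariate logistic regression, mediation analysis, and receiver operating characteristic (ROC) curve analysis" and says that the resulting biomarkers and model will serve the aim of "thereby providing evidence for the pathophysiological mechanisms underlying NEC progression".

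On timing, 3.3 records "CBC parameters, lactate levels, and parameters required for calculating the nSOFA score at the onset of NEC" and describes no earlier or repeat sample. These are the three domains that 1.2 proposes to combine. Section 1.1 says of lactate that "hyperlactatemia may arise from concurrent sepsis or perinatal asphyxia", and describes nSOFA as a tool to "objectively quantify the degree of organ dysfunction in critically ill neonates by evaluating the respiratory, cardiovascular, and hematologic systems".

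**The concern.** An indirect effect has a causal meaning only if the exposure precedes the mediator, the mediator precedes the outcome, and no uncontrolled common cause links them. The plan secures none of these.

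Two markers sampled at onset may both simply reflect how ill the infant is. They will then correlate with each other and with perforation or death, and the product of the two paths will differ from zero even if neither marker affects anything. The bootstrap interval measures sampling error in that product and does not detect the confounding.

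The markers are also unlikely to reflect severity equally, since nSOFA is built to measure organ dysfunction. The order that puts the better severity marker in the mediator role will then look supported and the reverse order will not, which gives a convincing but spurious direction.

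Because nothing is named, the exposure, mediator and outcome can be picked from the long marker list in 3.6 after the data are seen. What is at stake is a published mechanism that the data cannot support.

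**Working it through.** The plan gives no figure to reproduce: 3.2 states 220 infants without an event rate, effect size or power. The check is therefore a simulation in which no causal path exists.

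**From the documents:** n = 220 (3.2); 1,000 bootstrap resamples and two-sided 0.05 (3.7); binary primary outcomes, perforated NEC and in-hospital death (3.6).

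**Assumed:** event rate 20%, range 10 to 50%; severity log odds ratio 1.0 per SD, also 0.5 and 0; the marker loadings below. The documents do not fix the event rate. Section 3.4 requires "Diagnosis of NEC and having undergone surgical treatment", while the Abstract asks only for a diagnosis and 3.6 lists surgical NEC as an outcome.

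**Model:** severity S is standard normal. Exposure X = LX·S + noise and mediator M = LM·S + noise, each with unit variance. logit P(Y) = k + g·S. True X→M, X→Y and M→Y effects are all zero. A linear model for M gives path a, a logistic model for Y on M and X gives path b, and the percentile bootstrap interval for a·b is checked against zero. There are 400 datasets per cell (Monte Carlo error at most ±5 points).

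**Why the order matters.** Path a equals the marker correlation r = LX·LM in either order. Path b is roughly proportional to the weight on the mediator when S is regressed on both markers, LM(1 − LX²)/(1 − r²):

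- LX = LM = 0.5: r = 0.25; 0.5 × 0.75 / 0.9375 = 0.40 in both orders.
- LX = 0.35, LM = 0.8: r = 0.28; 0.8 × 0.8775 / 0.9216 = 0.76.
- Same pair swapped: 0.35 × 0.36 / 0.9216 = 0.14.

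The same correlation thus gives a product of 0.28 × 0.76 = 0.21 in one order and 0.28 × 0.14 = 0.04 in the other, with no causal path in either.

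**Share of datasets with a significant indirect effect (X→M order / swapped), g = 1.0:**

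| Loadings LX, LM | No covariate, 20% events | No covariate, 10–50% events | Covariate correlated 0.7 with S, 20% events | Covariate correlated 0.85 with S, 20% events |
|---|---|---|---|---|
| 0.5, 0.5 | 48.0% / 51.2% | 37–64% / 40–66% | 13.0% / 9.2% | 2.8% / 1.8% |
| 0.4, 0.6 | 73.5% / 25.3% | 54–88% / 21–37% | 21.5% / 6.8% | 2.5% / 1.0% |
| 0.35, 0.8 | 96.3% / 10.5% | 82–99% / 10–17% | 54.2% / 7.0% | 10.5% / 2.0% |

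With g = 0.5 and no covariate, at event rates of 10% and 50%, equal markers give 13–28%, and loadings 0.35/0.8 give 33–76% against 4–9% swapped. With g = 0, the rate is 3–9%. Separate runs of the 20% setting gave 48–57% for equal markers (X→M order) and, for 0.35/0.8, 96–98% against 11–14%.

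**Additivity.** If the outcome is binary and modelled logistically, direct plus indirect log-odds do not sum exactly to the total. With a direct log odds ratio of 0.5, path a of 0.3 to 0.5 and 20% events, the sum exceeds the total by 3–4% when the mediator log odds ratio is 0.5, and by 12–14% when it is 1.0. The bootstrap test of the indirect effect is not invalidated.

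**The case against.** The strongest reply is that the documents never say two onset markers will be exposure and mediator. Sections 3.3 and 3.6 also list gestational age, birth weight, Apgar score and chorioamnionitis, all of which precede onset. With one of these as exposure, the exposure–mediator order is known and the role-swapping argument falls away. That stands, and the simulated rates apply only to the onset-marker case. It does not rescue the analysis, because confounding between mediator and outcome remains and no adjustment is stated.

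A reader might infer that 3.1 rests its mechanism claim on mediation alone, so that dropping mediation would settle the matter. The text does not support this: it credits four methods together. Correlation, logistic regression and ROC analysis are associational too, so the wording would still be unsupported.

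A reader might also infer that the decomposition fails arithmetically in every case. It does not: the outcome is unnamed, and with a linear outcome model the paths add up.

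Finally, the percentages depend on assumed inputs, and a good severity covariate brings most of them below 5%. That is correct. Section 3.6 records possible proxies such as sepsis, shock and ventilation, but the plan does not commit to using any of them in the mediation models.

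**Conclusion.** The concern holds in conditional form. As written, the mediation analysis is unspecified and unadjusted. In the likely but unstated case of two onset markers, a significant indirect effect would show neither mediation nor direction.

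With 220 infants, 20% events, a severity log odds ratio of 1.0 and no covariates, a false indirect effect appears in about half of datasets for equal markers, and in about 96% against 11% by order for loadings 0.35/0.8. These figures illustrate what can happen and do not predict this study's results. They fall with weaker severity effects and with a good severity covariate.

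It would be too strong to conclude that the study's aim is compromised. Section 2 states a predictive objective, which rests on the logistic and ROC analyses and is not affected. Non-additivity on the log-odds scale is a minor point that applies only to a logistic outcome model.

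**What to change.** In 3.7 and the matching Abstract text, label the mediation analysis exploratory and associational, or drop it. In 3.1, replace the mechanism wording with a statement that the analyses describe associations and predictive performance. This change is needed even if mediation is dropped.

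If mediation is reported:

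- Name the exposure, mediator and outcome. If they were chosen after the data were examined, say so.
- Adjust both the mediator model and the outcome model for recorded pre-exposure covariates: those of gestational age, birth weight and asphyxia that are not the exposure. These do not fully capture severity at onset, so the result remains associational.
- Do not present a comparison of the two marker orders as evidence of direction.

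The cost is wording and a little analysis work, and the mechanistic claim is lost. Few events may limit the covariates: 220 × 0.10 = 22 events at a 10% rate and 220 × 0.20 = 44 at 20%. No new data are needed.

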### 3.2 Sample size

220 newborns who suffered from necrotizing enterocolitis between July 1, 2017 to December 31, 2022.

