### 3.6 Observation items

- (1). Baseline Characteristics: Neonatal demographics (sex, gestational age, birth weight, small for gestational age [SGA] status), maternal factors (mode of delivery, premature rupture of membranes, chorioamnionitis), neonatal birth history (1-min Apgar score  $\leq 7$ , intrauterine distress), and preterm complications (patent ductus arteriosus [PDA], respiratory distress syndrome [RDS], sepsis, shock), feeding pattern, and requirement for mechanical ventilation.

- (2). Laboratory and Clinical Assessment Indicators: Hepatobiliary function:

Albumin, albumin/globulin ratio, total bile acid; Hematologic and inflammatory parameters: White blood cell (WBC), absolute neutrophil (NEU), lymphocyte (LYM), monocyte (MON), eosinophil (EOS) counts, red blood cell (RBC), platelet (PLT) count, mean platelet volume (MPV), platelet distribution width (PDW), C-reactive protein (CRP), neutrophil-to-lymphocyte ratio (NLR), monocyte-to-lymphocyte ratio (MLR), neutrophil-to-monocyte ratio (NMR), systemic inflammatory index (SII), systemic inflammatory response index (SIRI), aggregate inflammatory systemic index (AISI); Metabolic: Serum lactate, blood glucose; Organ dysfunction assessment: Neonatal Sequential Organ Failure Assessment (nSOFA) score.

(3). Primary Outcome Indicators:

- Occurrence of perforated necrotizing enterocolitis (PNEC);
- In-hospital mortality.

(4). Secondary Outcome Indicators:

- Bell's staging of NEC;
- surgical NEC

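### If PNEC or in-hospital death is the mediation outcome, fitted logistic direct and indirect effects will not sum to the fitted logistic total, so the planned decomposition needs a defined effect scale

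*Combined protocol and SAP*

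**What the plan says.** Section 3.7 of the combined protocol and SAP states "Mediation analysis was performed using the PROCESS macro 4.1", "with 1000 bootstrap iterations to decompose the total effect into direct and indirect paths". The abstract repeats this. No exposure, mediator, outcome, covariate set or effect scale is given for the mediation analysis.

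Section 3.6 lists two primary outcomes: occurrence of PNEC and "In-hospital mortality". Both are yes/no. Of the two secondary outcomes, surgical NEC is also yes/no and Bell's stage is ordinal.

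The only regression that section 3.7 names for outcomes is logistic: variables below the 0.05 threshold "in univariate analysis were subsequently included in multivariate logistic regression analysis". Section 3.1 lists mediation among the methods used to "perform mutual analysis of the collected clinical data, laboratory parameters, and prognostic/mortality outcomes", and presents the results of these methods together as evidence on the mechanisms of NEC progression.

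Section 3.2 gives the sample as "220 newborns who suffered from necrotizing enterocolitis between July 1, 2017 to December 31, 2022", with no event rate or effect size.

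**The concern.** Splitting a total effect into a direct and an indirect part by regression coefficients relies on the identity c = c' + ab. Here a is the effect of exposure on mediator, b the effect of mediator on outcome given exposure, c' the effect of exposure given mediator, and c the effect of exposure without the mediator in the model. The identity is exact for least-squares linear regression. It is not exact for logistic regression. Adding a mediator that predicts the outcome changes the scale of the exposure's log-odds coefficient (non-collapsibility), so c and c' are not directly comparable. Naming the variables and adjusting fully for confounding does not remove this.

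At stake is the interpretation of the mediation result. If the total, direct and indirect coefficients are tabulated side by side, they will not add up. If a reader or author then forms a percentage, the answer depends on which formula is used, and some formulas can be far from any well-defined share. Section 3.1 intends the analyses to inform mechanism, so the effect scale matters.

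**Working it through.** **Inputs.** From the documents: binary primary outcomes (3.6), logistic regression (3.7), n = 220 (3.2). The plan states no mediation result, event rate or path coefficient, so it has no figure to reproduce. Everything below rests on assumed values, shown as ranges.

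**Model.** X is standard normal. M = aX + e, with Var(M) = 1. logit P(Y = 1) = i + c'X + bM, with i set to give the chosen event rate. Both models are correct and there is no confounding. The total c is the coefficient from the population logistic regression of Y on X alone, found by numerical quadrature.

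**Control.** With a continuous outcome and least squares, c' + ab − c is at most about 3 × 10⁻¹⁵ in every simulated data set. The identity holds there, as expected.

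**Logistic case, a = c' = 0.5.** Shortfall = 1 − c/(c' + ab).

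| Event rate | b | c | c' + ab | Shortfall |
|---|---|---|---|---|
| 1% | 0.5 | 0.748 | 0.750 | 0.3% |
| 1% | 1.5 | 1.172 | 1.250 | 6% |
| 20% | 0.5 | 0.727 | 0.750 | 3% |
| 20% | 1.5 | 0.998 | 1.250 | 20% |
| 30% | 1.0 | 0.880 | 1.000 | 12% |
| 30% | 1.5 | 0.976 | 1.250 | 22% |

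Over a = 0.3–0.5, b = 0.5–1.5, c' = 0 or 0.5 and event rates of 20–40%, the shortfall runs from about 3% to 27%. The top of the range is full mediation (c' = 0) with a = 0.3, b = 1.5 and 40% events. There ab/c = 1.37, so the shortfall is 1 − 1/1.37 = 27%, and ab/c would report 137% mediated.

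**Effect on percentages.** Take a = 0.3, b = 1.5, c' = 0.5, event rate 40%:

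- ab = 0.3 × 1.5 = 0.450; c' + ab = 0.950; fitted c = 0.699; shortfall = 1 − 0.699/0.950 = 26%.
- ab/c = 0.450/0.699 = 64%.
- (c − c')/c = 0.199/0.699 ≈ 29%.
- ab/(ab + c') = 0.450/0.950 = 47%.
- Natural indirect effect as a share of the total, risk-difference scale: 48%.

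Further cases with a = c' = 0.5:

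| Event rate | b | ab/c | (c − c')/c | ab/(ab + c') | Natural, log-odds | Natural, risk difference |
|---|---|---|---|---|---|---|
| 1% | 0.5 | 0.334 | 0.331 | 0.333 | 0.333 | 0.417 |
| 30% | 0.5 | 0.346 | 0.309 | 0.333 | 0.333 | 0.354 |
| 30% | 1.0 | 0.568 | 0.432 | 0.500 | 0.497 | 0.525 |
| 30% | 1.5 | 0.768 | 0.488 | 0.600 | 0.596 | 0.626 |

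For a = c' = 0.5, at every event rate from 1% to 50%, ab/(ab + c') stays within about 0.01 of the natural log-odds share. It can differ more from the risk-difference share when the outcome is rare, because that is a different scale.

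**No mediation.** With a = 0, b = 1, c' = 0.5 and 30% events, c = 0.422, so (c − c')/c = −0.18. The difference method shows a negative mediated share where there is no mediation.

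**At the planned size.** In 1,000 simulated data sets with n = 220, about 30% events, a = c' = 0.5 and b = 1.0, the mean of c' + ab was 1.019 and the mean of c was 0.891. The sum exceeded c in every data set.

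**After the fix.** Natural direct and indirect effects add to the total, with a residual below 10⁻¹⁸ on the risk-difference scale. They also add on the log-odds scale.

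**The case against.** Four points can be made for the plan.

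*The mediation outcome is not stated.* This stands. PNEC or death is a strong inference from sections 3.1 and 3.6, not a quoted fact. With a continuous outcome, such as the "Neonatal Sequential Organ Failure Assessment (nSOFA) score" treated as numeric, the identity would be exact. Section 3.6 lists that score as an assessment indicator, however, and no listed outcome is continuous. The point is therefore conditional.

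*A reader might infer that any proportion mediated would be wrong.* The figures do not support that. ab/(ab + c') gives 47% against 48% in the worked case and tracks the natural log-odds share closely. Only ab/c and the difference method are shown to mislead. The plan also never promises a proportion, and section 3.1 offers no mediated shares, so harm from a percentage is a risk of how results are reported and not something the plan commits to.

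*The larger gaps need strong effects.* This also stands. b = 1.5 is an odds ratio of about 4.5 per SD of mediator. At b = 0.5 the shortfall is about 3–5%, and sampling error matters more: with n = 220, a = 0.3, b = 0.5 and 30% events, ab/(ab + c') itself ranged from 0.08 to 0.54 in 95% of simulated data sets. But the plan gives no ground for assuming weak effects or rare outcomes, and section 3.4 restricts inclusion to surgically treated infants.

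*Reporting direct and indirect paths with bootstrap intervals is already acceptable.* It is, and it is close to the second option below. What remains is the stated aim of decomposing a total effect, which separately fitted logistic coefficients do not achieve.

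**Conclusion.** The point holds conditionally. If PNEC or in-hospital death is the mediation outcome and is modelled by logistic regression, the fitted total will not equal the sum of the fitted direct and indirect effects. The shortfall is about 3–27% for a = 0.3–0.5, b = 0.5–1.5, c' = 0 or 0.5 and event rates of 20–40%. It is under 1% for a 1% event rate with b = 0.5. All these values are assumptions, because the documents give none.

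The direction was consistent wherever b was non-zero: c fell below c' + ab. The practical consequence is limited to how a total effect, or a percentage built from it, is reported and read; the indirect path ab and its bootstrap interval can still be reported on the log-odds scale. The plan should be changed, because the stated decomposition fails on the scale that the plan points to and the correction is cheap.

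**What to change.** In section 3.7 and the abstract, state the mediation outcome and the effect scale, then take one of two routes for PNEC and death.

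1. Preferred: estimate natural direct and indirect effects that add to the total. One example is risk differences by standardisation from the mediator model and the logistic outcome model, with bootstrap intervals. Natural effects on the log-odds scale would also add.
2. If PROCESS is kept: remove the claim that the total effect is decomposed. Report only ab and c' on the log-odds scale with bootstrap intervals, and no percentage from ab/c or from the difference method.

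The cost is a few lines of SAP wording, plus a short script for the first route. No new data are needed.

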## 1.2 Creativity

To address these gaps, the present retrospective cohort study aims to explore the potential predictive value of integrating metabolic (lactate), hematologic (CBC), and organ dysfunction (nSOFA) metrics for NEC and its associated mortality in preterm infants. By combining these complementary markers, we aim to overcome the

limitations of single biomarkers and fill the knowledge gap regarding risk stratification for perforated NEC—an outcome that holds profound implications for clinical decision-making and improving the survival rate of preterm infants.

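### If the combined marker is fitted by logistic regression, its AUC and its gain over nSOFA or lactate alone will be reported too high, because no optimism correction is planned

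*Combined protocol and SAP*

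**What the plan says.** Variables that reach p < 0.05 "in univariate analysis were subsequently included in multivariate logistic regression analysis" (Section 3.7, repeated in the Abstract). The next performance step is: "Receiver operating characteristic (ROC) curve analysis was conducted using SPSS 26.0 to evaluate the predictive performance of individual and combined biomarkers". The Abstract gives the same purpose, "to evaluate the predictive performance of individual and combined biomarkers". The one use of resampling belongs to the mediation analysis, run "with 1000 bootstrap iterations to decompose the total effect into direct and indirect paths".

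Sections 3.1 and 3.2 describe a single retrospective cohort of 220, and Section 3.1 names a predictive model as an aim. No hold-out sample, cross-validation, optimism correction or external cohort appears.

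What is combined is only partly described. Section 1.2 speaks of "integrating metabolic (lactate), hematologic (CBC), and organ dysfunction (nSOFA) metrics" without naming a CBC variable. Section 1.1 points to another pairing: "the combined utility of lactate levels and peripheral WBC profiles for NEC diagnosis and prognostic stratification remains unexplored". Section 3.7 could mean the screened model itself. No expected number of PNEC cases or deaths is given.

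**The concern.** The rationale rests on single markers falling short. On lactate, Section 1.1 says: "However, lactate alone lacks specificity". On nSOFA: "However, single nSOFA lacks sufficient sensitivity for severe NEC subtypes like PNEC-specific risk stratification". Section 1.2 then proposes to overcome this by combining markers. The difference in AUC between the combination and nSOFA or lactate alone is therefore what a reader will look for first, although the plan does not list it as an endpoint.

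A model fitted to 220 infants and scored on the same 220 looks better than it will in new patients. Screening on those data adds to this. A single marker named in advance and used as measured has almost no such advantage. The optimism in the combined AUC therefore passes almost entirely into the apparent gain, and the planned output gives no means of separating it from a real gain.

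**Working it through.** **Nothing to reproduce.** The sample size of 220 is stated without a calculation, and no AUC, AUC gain or event rate is given. The check is therefore a simulation with n = 220.

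**Inputs from the documents.** n = 220 (Sections 3.1, 3.2); screening at p < 0.05 (Section 3.7); candidates in Section 3.6, by my count 15 baseline + 22 laboratory and score items = 37.

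**Assumed inputs.** Event rates of 10–60%, marker strengths and correlations. Section 3.4 admits only surgically treated infants, whereas the Abstract does not. If Section 3.4 governs, PNEC could exceed 40%, so the range goes to 60%.

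**Events per coefficient.** Events are 220 × 0.10 = 22, × 0.20 = 44, × 0.40 = 88. Per coefficient of a three-marker model: 22/3 = 7.3, 44/3 = 14.7, 88/3 = 29.3. Per candidate in a 22-item screen: 1, 2, 4. In a 37-item screen: 0.6, 1.2, 2.4. At 60% the smaller group is again 88.

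**Quantity computed.** Overstatement = (apparent AUC of combination − apparent AUC of nSOFA) − (the same difference in new patients).

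**Set-up A.** Normal markers, 1,000 datasets per cell, exact new-patient AUC Φ(w′δ/√(2w′Σw)), where w are the fitted weights, δ the mean differences and Σ the covariance. True AUC of nSOFA 0.75; lactate 0.70, or 0.50 in one scenario; event rates 10–40%. With only nSOFA informative, gain over nSOFA as apparent / real / overstated (differences of 0.001 are rounding):

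| Events | Fixed 3 markers | 22-item screen | 37-item screen |
|---|---|---|---|
| 22 (10%) | 0.013 / −0.014 / 0.027 | 0.031 / −0.032 / 0.063 | 0.049 / −0.046 / 0.095 |
| 44 (20%) | 0.007 / −0.007 / 0.015 | 0.019 / −0.018 / 0.037 | 0.031 / −0.029 / 0.061 |
| 88 (40%) | 0.005 / −0.005 / 0.011 | 0.013 / −0.013 / 0.026 | 0.022 / −0.021 / 0.042 |

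Over all scenarios the overstatement was 0.008–0.027, 0.019–0.066 and 0.025–0.095 respectively. Mean apparent AUCs of the pre-named markers were unbiased: nSOFA 0.745–0.755 against 0.750, lactate 0.696–0.704 against 0.700.

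**Set-up B.** 13 binary and 24 continuous candidates, lactate–nSOFA correlation 0.3, log-OR per SD 0.45, 0.9 or 1.3, 300 datasets per cell, 20,000 new patients, event rates 10–40%.
- Fixed model of lactate, NLR and nSOFA: from 0.004 upwards. The largest cell (log-OR 0.45, 10% events) gave 0.057 − 0.005 = 0.052, but on repeat 0.050 − 0.015 = 0.035. Two other runs at that signal and event rate gave 0.032 and 0.036. About 0.04 is therefore a fair upper figure.
- The same fixed model against lactate alone: 0.002–0.03.
- 37-item screen: from 0.087 − 0.066 = 0.021 (log-OR 1.3, 40%) to 0.093 − (−0.048) = 0.141 (log-OR 0.45, 10%).

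**Set-up C.** 250 datasets per cell, event rates 10–60%: fixed 0.007–0.037; 22-item screen 0.018–0.092; 37-item screen 0.03–0.13. A further run of the weakest 10% cell gave 0.095 (22 items) and 0.134 (37 items). In a separate run at 60% events the fixed model's overstatement was 0.008–0.012.

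**When nothing adds to nSOFA.** The fixed model had the higher apparent AUC in 83–90% of datasets across runs, yet was 0.006–0.017 worse in new patients. The mean apparent gain was 0.007–0.016 in set-up B.

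**Does the correction work?** Corrected AUC = apparent AUC − mean over resamples of (AUC of the resample's model in the resample − its AUC in the full data).
- Fixed model: in set-up A at 20% events, apparent 0.781, corrected 0.767, true 0.767. In set-up B the corrected gain lay within 0.005 of the real gain, or within 0.013 when the CBC variable was picked from the data.
- Screened model with the screen repeated in each resample: in set-up A, apparent 0.813, corrected 0.757, true 0.774. In set-up B the corrected gain was off by −0.023 to +0.022.

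**The case against.** **The link is inferred.** The plan never says that the combined marker is the logistic model, or that the same infants fit and score it. It already uses fixed formulas such as SII, SIRI and AISI, and a fixed formula carries no fitting optimism. This stands: the point is conditional on a fitted combination. That remains the likeliest reading, because logistic regression is the only route to a multivariable combination that the plan names and no other data are described.

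**The size may be small.** This also stands in part. With a fixed three-marker model and only nSOFA predictive, the apparent gain exceeded 0.02 in just 30%, 13% and 6% of datasets at 10%, 20% and 40% events. A reader might infer that gains of 0.13–0.14 are typically spurious. The documents do not support that: it requires screening sex, delivery mode, feeding pattern and the rest into a model that Section 3.7 describes as one of biomarkers, with weak signal and few events.

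**The comparator matters.** A reader might extend the upward bias to any single marker. It does not extend to a best single marker picked in the same data, which carries its own selection optimism. Against that comparator, set-up B had the fixed model's gain understated by 0.007–0.048.

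**A strict claim rule would go too far.** One might want a gain claimed only when the interval for the AUC difference excludes 0. In set-up B, with lactate truly adding (log-OR 0.45–0.9), a corrected interval met that rule in only 4–16% of datasets at 10% events and 11–70% at 40%. I do not recommend it.

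**The aims are exploratory.** Section 1.2 is worded that way. This limits the severity but does not remove the bias.

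**Conclusion.** The point holds in conditional form. If the combination is fitted by logistic regression, the plan as written gives an upwardly biased AUC and an upwardly biased gain over pre-named nSOFA or lactate. The direction was the same in every set-up. The size is less certain, because event rates, marker strengths, correlations and the combination itself are all assumed.

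For the gain over nSOFA, the overstatement is about 0.004–0.04 for a fixed model of lactate, one CBC index and nSOFA, and about 0.02–0.09 for a screen of the 22 laboratory and score items. The 37-item figure of 0.13–0.14 is an extreme case. A real contribution of lactate is not ruled out; the planned output simply cannot distinguish it from optimism. This should be fixed and is a cheap improvement.

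**What to change.** In Section 3.7, for PNEC and in-hospital mortality separately:

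1. State which markers form the combined model and whether they were chosen before the data were seen. Include the Section 1.2 combination (lactate, one named CBC index, nSOFA), fitted without univariate screening and compared with nSOFA alone and with lactate alone.
2. For every fitted combination, report the apparent AUC beside the bootstrap optimism-corrected AUC and the corrected AUC difference (500–1,000 resamples). Repeat any screening or index selection inside each resample, and base conclusions on the corrected values.
3. If the model is fixed in advance, also report the likelihood-ratio test of adding lactate and the CBC index to nSOFA. In set-up B at 10%, 20% and 40% events it reached p < 0.05 in 31%, 61% and 75% of datasets (log-OR 0.45) and in 87%, 99% and 100% (log-OR 0.9), against 5–7% when nothing added.
4. Label the p < 0.05-screened model exploratory, and note that its corrected gain can be about 0.02 off in either direction.

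The cost is a lower stated AUC and some scripting beyond the SPSS, PROCESS and GraphPad software named in the plan. No new patients or data are needed.
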